1.0 Objectives

Assess the effectiveness of adding episodic future thinking (EFT) to our standard behavioral weight control program to improve weight loss, DD, working memory, glycemic control (HbA1c) and behavioral and/or medication adherence over a 6 month period in persons with prediabetes.

2.0 Hypotheses

Specific Aim 1: To determine whether change in weight loss is superior for those with prediabetes randomized to behavioral treatment for obesity + EFT (BT-EFT) versus behavioral obesity treatment (BT). We hypothesize that weight loss for BT-EFT will be superior to BT after 6 months of treatment.

Specific Aim 2: To determine whether change in HbA1c is superior for those with prediabetes randomized to behavioral treatment for obesity + EFT (BT-EFT) versus behavioral treatment (BT). We hypothesize that reductions in HbA1c for BT-EFT will be superior to BT after 6 months of treatment.

Specific Aim 3: To determine whether change in DD is superior for those with prediabetes randomized to behavioral treatment for obesity + EFT (BT-EFT) versus behavioral treatment (BT). We hypothesize that reductions in DD for BT-EFT will be superior to BT after 6 months of treatment.

Secondary Aim 1: To determine whether change in medication and behavioral adherence for hypertension and/or hyperlipidemia medications is superior for those with prediabetes randomized to behavioral treatment for obesity + EFT (BT-EFT) versus behavioral treatment (BT). We hypothesize that medication and behavioral adherence for BT-EFT will be superior to BT after 6 months of treatment.

Secondary Aim 2: To determine whether improvements in working memory are superior for those with prediabetes randomized to behavioral treatment for obesity + EFT (BT-EFT) versus behavioral treatment (BT). We hypothesize that working memory improvements for BT-EFT will be superior to BT after 6 months of treatment.

Exploratory Aim 1: To examine the relationship between baseline DD and DD change with weight loss, improvements in HbA1c and medication adherence. We hypothesize that baseline DD and DD change will predict weight loss, improvements in HbA1c and medication adherence.

3.0 Scientific Endpoints

The primary endpoint is the reduction of discounting of the future, weight loss, and improved glycemic control.

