14.0 Statistical Analysis Plan

Analytic plan is to use factorial ANCOVA to compare between group differences in different measures of DD, executive function, weight loss, changes in metabolic control, dietary composition, and physical activity for subjects randomly assigned BT-EFT/BT. Covariates will be used if significant differences between groups are observed in subject characteristics. We predict a main effect of EFT such that EFT will reduce the discounting, improve metabolic control, and increase weight loss compared to BT subjects.

The estimated sample size for this study is based on an ESD for reducing DD of 0.72 in obese/overweight subjects. In our pilot study of EFT vs control in a weight control program we observed even larger ESD of 1.64 for weight and 1.04 for energy intake. Based on ESD = 0.72 for DD, using power of 0.80 and alpha of 0.05, we can detect differences between groups in DD with 32 subjects per group, 64 total. Since we are anticipating 20% attrition for the field study, we will recruit 78 persons with prediabetes to start.

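### Three primary outcomes are tested with no multiplicity or success rule and no designated delay-discounting measure; the stated alpha and power cover one delay-discounting test only

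*Combined protocol and SAP*

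**What the plan says.** Section 3.0 (Scientific Endpoints) puts three outcomes under one primary endpoint: "The primary endpoint is the reduction of discounting of the future, weight loss, and improved glycemic control".

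Section 2.0 (Hypotheses) splits them into three Specific Aims, each with its own hypothesis:
- Aim 1: "We hypothesize that weight loss for BT-EFT will be superior to BT after 6 months of treatment"
- Aim 2: "We hypothesize that reductions in HbA1c for BT-EFT will be superior to BT after 6 months of treatment"
- Aim 3: "We hypothesize that reductions in DD for BT-EFT will be superior to BT after 6 months of treatment"

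Section 14.0 (Statistical Analysis Plan) is the whole analysis plan. It proposes "factorial ANCOVA to compare between group differences in different measures of DD, executive function, weight loss, changes in metabolic control" and some further outcomes, and predicts that "EFT will reduce the discounting, improve metabolic control, and increase weight loss compared to BT subjects". The sample size rests on DD: "Based on ESD = 0.72 for DD, using power of 0.80 and alpha of 0.05, we can detect differences between groups in DD", at 32 per group. For weight it cites a pilot, in which "we observed even larger ESD of 1.64 for weight and 1.04 for energy intake". It gives no effect size for HbA1c.

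No section ranks the three outcomes, says whether one or all must succeed, or mentions multiplicity. Section 12.0 (Measurements) permits two DD tasks and several commodities and designates none of them.

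**The concern.** Two choices are left open that determine what a positive trial means: how the three primary outcomes combine, and which version of DD counts. The plan does not say when either will be settled. Section 21.0 lists interim analyses among the topics of regular study meetings and provides for interim results to be communicated, so nothing in the text prevents these choices from being made with results in view. That is a gap in protection, not evidence of intent.

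The consequence depends on the rule. If any one outcome can carry a claim, the trial's false-positive risk exceeds the only alpha stated. If all three must succeed, the stated power does not describe that decision.

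**Working it through.** **Inputs from the documents.** Section 14.0: DD effect 0.72 SD, alpha 0.05, power 0.80, 32 per group, pilot weight effect 1.64 SD. Section 6.0: about 80 completers, taken here as 40 per arm. **Assumed, because the documents give neither:** the HbA1c effect and the correlations between outcomes (0 to 0.9, equal for all pairs).

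**1. The plan's own figure.** Normal approximation, two-sided: n = 2(1.960 + 0.842)² / 0.72² = 30.3, so 31 per arm. The two-sample t-test gives 31.27, so 32 per arm, with power 0.809. A one-sided t-test would need 25. The plan does not state sidedness, but its 32 per group is exactly one two-sided DD test.

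**2. If each outcome may support its own claim at 0.05.** With independent outcomes, the chance of at least one false positive is 1 − 0.95³ = 0.143. Simulated correlated normal statistics give 0.125 at correlation 0.5, 0.109 at 0.7 and 0.084 at 0.9. Counting only false claims in favour of EFT, the range is 0.073 (correlation 0) to 0.042 (0.9), against 0.025. If DD may be claimed on either of two versions, the two-sided figure runs from about 0.09 (all correlations 0.9) to 0.18 (0.5 between the versions, 0 elsewhere).

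**3. If all three are required at 0.05.** At correlation 0, joint power is the product of the three powers. Weight power exceeds 0.999 at 1.64 SD, so DD and HbA1c decide the result. The upper end of each range is the simulated value at correlation 0.9.

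| Per arm | HbA1c effect (assumed) | DD power | HbA1c power | Joint power, correlation 0 to 0.9 |
|---|---|---|---|---|
| 32 | 0.5 | 0.809 | 0.504 | 0.41-0.50 |
| 32 | 0.72 | 0.809 | 0.809 | 0.65-0.76 |
| 40 | 0.5 | 0.889 | 0.598 | 0.53-0.60 |
| 40 | 0.72 | 0.889 | 0.889 | 0.79-0.85 |

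At 32 per arm, HbA1c alone has 80% power only for an effect of about 0.71 SD.

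**4. DD power if alpha is controlled.**
- Holm, worst case (DD tested at 0.05/3 = 0.0167): 0.66 at 32 per arm, 0.78 at 40.
- Holm with weight at the pilot effect: weight is almost always rejected first, so DD is tested at 0.025 or better. Power is about 0.72-0.79 at 32 per arm for an HbA1c effect of 0 to 0.72, and 0.82-0.88 at 40.
- Fixed order, weight then DD: above 0.999 × 0.809, about 0.81 at 32 per arm.
- Fixed order by aim number (weight, HbA1c, DD): DD is reached only if HbA1c succeeds, so its power is the joint power in step 3.
- Fixed order, DD first: weight is blocked 1 − 0.809 = 19% of the time.

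**5. Which DD measure.** Section 11.0 collects DD at baseline, 3 and 6 months. Its schedule table lists a cued DD assessment on a separate row, which starts after randomization. Cues are generated only after randomization, at about week 6, and only in BT-EFT. A cued assessment therefore has no cued baseline and no like-for-like control. The task, commodity and amount remain open, and so does the optional cue presentation that Section 12.0 allows within the adjusting-amount task.

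**The case against.** The strongest reply is that Section 2.0 sets out three separately numbered questions, apart from the secondary and exploratory aims. On that view each is answered at its own 5% level, and familywise control is a matter of judgement. No section says that one success out of three makes the trial positive. A reader might infer from the 14.3% that the trial's type I error is inflated to that level; the documents do not support this, because they never state the rule that produces it. What remains is that Section 3.0 binds the same outcomes into one primary endpoint, and three unadjusted primary tests are what the text yields if followed as written.

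A second reply is that the joint wording of Section 3.0 and the joint prediction in Section 14.0 imply that all three must succeed, which would protect alpha. A prediction is not a success criterion, however, and that rule would need a power statement that includes HbA1c.

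Three other points stand in the plan's favour. The sample size is correct for DD. Weight is amply powered at the pilot effect. The 6-month time point is fixed in all three hypotheses. A reader might also infer that cued and uncued DD are equally open as the primary measure. The schedule and the timing of the cues point largely to the uncued assessment, even though no sentence says so.

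**Conclusion.** The point holds as a cheap improvement. Two facts need no assumption: the plan has no rule for its three primary outcomes, and it designates no single DD measure. Its alpha of 0.05 and power of 0.80 describe one DD test.

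The size depends on the rule that is adopted. With separate claims, familywise error lies between 8.4% and 14.3% over the correlations shown, and is higher if several DD versions can count. With all three required, error is controlled, and power turns on an HbA1c effect that the plan does not give. At an assumed 0.72 SD with 40 per arm, joint power is close to or above 0.80; at 0.5 SD it is well below 0.80 at either sample size. All power figures use unadjusted t-tests and assume that the DD and pilot weight effects are true.

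The documents do not support saying that the sample size is wrong for DD, that weight is underpowered, or that the trial will claim success on any single outcome.

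**What to change.** 1. **Section 3.0:** before any between-group results are examined, designate one DD measure (task, commodity and amount), taken without cues at the primary assessment session, where DD has a baseline and is comparable between arms. Report cued DD and all other versions as secondary.
2. **Section 14.0:** because Section 2.0 states three separate superiority hypotheses, control overall two-sided alpha at 0.05 across them. Use either Holm (smallest p-value against 0.0167, next 0.025, largest 0.05, stopping at the first failure) or a prespecified fixed order, such as the aim numbering or weight followed by DD. If the sponsor instead requires all three, say so and restate power with a stated HbA1c effect size.
3. **Section 14.0, sample size:** restate the power as applying to DD under the chosen rule.

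The change is to text only and needs no new data. The price is DD power under Holm (step 4 of the working) or, under a fixed order, the loss of confirmatory status for later outcomes once an earlier one fails. The aim order is the expensive one for DD, because HbA1c stands before it. Restoring 0.80 for DD in the Holm worst case would take 42 per arm, that is 84 completers, or 84 / 0.8 = 105 recruited against the planned 78. That is not proposed; an honest power statement is enough.

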4.0 Background & Significance

DD has been related to several adverse health behaviors including smoking (Bickel et al., 1999) and obesity (Rollins et al., 2010). Our laboratories have extensive experience collecting information about DD and these various health outcome behaviors.

Initial research on Type 2 diabetes (T2D) using a brief monetary choice questionnaire showed T2D individuals who discount the future have worse metabolic control than those who delay gratification (Reach et al., 2011). To our knowledge, there has been no research on the effects of EFT on DD among patients with prediabetes.

Adults with greater DD is associated with obesity (Appelhans et al., 2012), and low activation of brain sites critical for self-control in DD predicts longitudinal weight gain in adults (Kishinevsky et al., 2012). Likewise, inability to delay gratification predicts greater subsequent weight gain in young children (Francis and Susman, 2009) and poorer response to evidence-based pediatric weight control programs (Seeyave et al., 2009).

In turn, the prevalence of T2D is associated with obesity (Kahn et al., 2006). Moreover, T2D (Vahanen et al., 1997, Kanaya et al., 2004, Yaffe et al., 2004) and risk for T2D (Vahanen et al., 1997) are associated with increased risk of executive dysfunction. This association suggests one of two possibilities: (1) diabetes causes a decline in executive function, or (2) inadequate executive function contributes to obesity and then diabetes. In either case, the relationship between executive function and both obesity and diabetes can present challenges in adhering to behavioral and medical therapies (Smith et al., 2011, Primožič et al., 2012). Poor planning, low working memory, cognitive inflexibility, poor attention to detail in combination with excessive DD can lead to weight gain and poor metabolic outcomes.

Research supports Episodic Future Thinking (EFT), self-projection into the future to pre-experience an event (Atance & O'Neill, 2001), as an effective approach to reduce bias towards immediate gratification (Daniel & Epstein, 2013; Daniel, Stanton, & Epstein, 2013). However, little is known about EFT's effect in individuals at risk for Type 2 Diabetes. Understanding the effect of EFT in prediabetics can be efficacious in translating this technique into an efficacious health intervention.

5.0 Study Design

This study is an experimental between-subjects design; subjects will be randomized to Behavioral Treatment for obesity + Episodic Future Thinking (BT-EFT) or control group Behavioral Treatment for obesity (BT).

6.0 Local Number of Subjects

Up to 200 subjects will be enrolled at the University at Buffalo (up to 400 nationally). The second site is located at Virginia Tech Carillon Institute, local PI, [name]. We expect about 25% of participants to meet our in-lab screening criteria, 20% of those participants subjects to drop out and about 80 subjects will complete the study. In addition, a small sample (approximately 4-6

subjects) will be assigned to be pilot participants to help with quality assurance and data validity procedures. Participants will be informed if they are a pilot participant at the time of consent.

7.0 Inclusion and Exclusion Criteria

Inclusion:

Participants must be 18 years of age or older to participate.

Prediabetes: Participants must have a diagnosis of prediabetes within the last 2 years or meet criteria for prediabetes. The American Diabetes Association guidelines (Group, 2003) defines prediabetes as Fasting Plasma Glucose (FPG) 100-125 mg/dl, 2h glucose 140-199 mg/dl after Oral Glucose Tolerance Test (OGTT), or hemoglobin A1c (HbA1c) approximately 5.4-6.7%.

Exclusion:

Type 2 Diabetes: Individuals will be excluded if they have Type 2 Diabetes.

Pregnancy: Women who are pregnant or lactating will be excluded from participation.

Substance use, abuse, or dependence: Individuals that currently have problems with substance dependence, addiction, or problematic substance use that would limit participation (e.g., binge drinkers, alcoholics, daily stimulant/opiate users) will be excluded.

Conditions that affect adherence: Participants should not have a condition that would limit participation which include medical conditions that would affect individuals' ability to use the computer for prolonged period of time; leave the individual unable to ambulate; or current diagnoses of an eating disorder other than binge-eating disorder (anorexia, bulimia), unmanaged psychiatric disorder (depression, anxiety, attention deficit hyperactivity disorder (ADHD), schizophrenia), or an intellectual impairment that would impact study adherence. Additionally, participants should be able to attend to all or most group and individual sessions. If a participant is not able to make most sessions (e.g. participant is out of town for several days or weeks during the study (e.g. work or vacation travel)) they may be excluded from the study

Abnormal glucose related to medications: Participants should not be taking medications that would limit participation and cause abnormal glucose levels (e.g. atypical antipsychotic medications or glucocorticoids) including diabetic drugs such as Metformin.

Prior participation in similar studies: Individuals who have recently participated in a laboratory study using similar methods may also be excluded.

Recent changes in weight: Individuals should not have had any significant changes in weight (e.g. 10% change) prior to starting this study.

8.0 Vulnerable Populations

- N/A:** This research does not involve pregnant women.
- N/A:** This research does not involve non-viable neonates or neonates of uncertain viability.
- N/A:** This research does not involve prisoners.
- N/A:** This research does not involve persons who have not attained the legal age for consent to treatments or procedures (“children”).
- N/A:** This research does not involve cognitively impaired adults.

9.0 Eligibility Screening

Interested participants will have the opportunity to complete an initial screening by phone, online, or paper upon their preference to determine if they meet the inclusion criteria as previously described. Information about the study will be provided and consent will be obtained to prescreen for eligibility purposes. Additionally, we may send the person a link to a video that explains what the purpose of the study is and what can be expected.

During the prescreen, along with other screening questionnaires participants will also complete the PHQ-2, a shorter version of the PHQ-9, which measures current (within the past two weeks) feelings of depression or loss of interest in activities. Those that score a 3 or above on the PHQ-2, will be contacted for follow-up via phone or in person at the screening session by a trained research staff member and be given the remainder of the PHQ-9. The PHQ-9 is a validated measure that looks not only at feelings of depression and associated symptoms, but also assesses for thoughts of self-harm. Given the concern for having a participant indicate thoughts of self-harm, this procedure would allow for a real-time conversation with that participant to monitor responses and also provide them with appropriate resources. Additionally, if the participant appears to be extremely upset and/or emotional, we may ask them to fill out the Beck Depression Inventory (BDI), a reliable measure of assessing depression (Sprinkle et. al. 2002).

As part of the prescreen survey, prospective participants will also complete the Three Factor Eating Questionnaire (TFEQ) (Stunkard & Messick, 1985), a validated instrument to detect dietary restraint (Allison, Kalinsky, & Gorman, 1992) with three subscales that assess dietary restraint, hunger, and disinhibition. A short revised version, the Three factor eating questionnaire-R18 (TFEQ-R18), measures 3 aspects of eating behavior: cognitive restraint, uncontrolled eating, and emotional eating (Karlsson, Persson, Sjöström, & Sullivan, 2000). After completing the prescreen survey, responses will be reviewed by research staff to assess eligibility. Participants will be called, emailed, or mailed a letter (depending on their preferred method of contact provided in the prescreen survey) regarding their eligibility. Those who are eligible will be scheduled to come into our lab for an in person screening visit (session 1).

At the in person session 1 screening appointment, all participants will be given the Eating Disorder Examination (EDE) Questionnaire which is a well-established

and valid measure for eating disorders (J.M Mond et. al. 2004). If it is determined that they may have an eating disorder other than binge-eating disorder, the participant will not be eligible to continue with the study, and their physician may be notified. Binge-eating disorder or binge-eating disorder symptomology will not be considered exclusionary as behavioral weight loss treatment is both safe and effective for individuals with binge-eating disorder and binge-eating disorder symptomology (Grilo et al., 2011; Munsch et al., 2007). All participants who complete the EDE will be provided with a list of resources.

At the in person screening visit (session 1) documented consent will be obtained from potential participants. During the screening procedure, participants will be asked to sign a medical release form allowing the primary care physician to provide us with the information regarding eligibility and also allow us to send any pertinent medical information to their primary care physician (i.e. diagnoses of obesity, prediabetes, hypertension, dyslipidemia, depression score assessed by the BDI). If we do not receive the form within about 5 business days we will call to follow up with the primary care physician. Participants will also be asked to sign a release form for relevant pharmaceutical records (e.g. refill history of medications used to treat pre-diabetes, diabetes, and/or hyperlipidemia and hypertension) from their current pharmacy. Release of pharmaceutical records may be attained through the end of study participation if not attained at screening and will cover the period from about 90 days prior to screening to about the end of study participation. At the screening visit, participants will have their HbA1c levels measured by finger stick to obtain a drop of blood. If subjects meet eligibility criterion based on HbA1c levels (approximately 5.4% - 6.7%) at the initial screening visit, they may be eligible to participate regardless of confirmatory PCP diagnosis. Additionally, participants will be assessed for hyperlipidemia by finger stick and blood testing as well as for hypertension using an automated blood pressure machine.

Additionally at the first visit, participants may provide us with a urine sample to check for recent substance use and for pregnancy status for females. If the pregnancy results are positive the participant will be informed and they will not be eligible to continue with study. If throughout the study there is reason to believe a participant has become pregnant (i.e. the participant expresses that is their belief), we will provide pregnancy testing. If the pregnancy results are positive, the participant will be informed and they will not be eligible to continue with the study.

Finally, at the in person screening visit (session 1), participants will have their responses to the prescreen eligibility survey reviewed with a research team member to follow up on any items or any new discoveries that may affect adherence to the study program. At the completion of the screening visit, participants will not know if they are eligible to continue, and all of the information gathered from the participant will be reviewed with all study team members to make a mutual decision if the participant will likely be able to successfully adhere to all study procedures (e.g. attend all study sessions). After that decision is made by the research team, the participant will be followed up

with by phone or email (or participant's preferred method of contact) within one week regarding their eligibility. If eligible to continue, participants will then be scheduled for the baseline assessment session.

Study personnel will inform participants that this information will be used to communicate with them about study eligibility and that this information will be kept confidential and not shared with anyone outside of the study team.

The information assessed during screening is recorded in a secure database that requires a password to enter. The database is used by all members of the Division of Behavioral Medicine and has been approved for use by previous IRB committees. Information is retained in the database only if the subject gives consent.

